3.8. TREATMENT ASSIGNMENT & BLINDING

3.8.1. Treatment Assignment

Potential study subjects will be screened and assigned a subject number. Once all screening procedures are completed and the study eligibility is confirmed by the investigator, the randomization numbers will be allocated to subjects within the appropriate treatment arm by the randomization system. Once a screening or randomization number has been assigned, it will never be re-used. No subjects will be randomized into the study more than once. If a randomization number has been allocated incorrectly, no attempt will be made to remedy the error once study medication has been dispensed. The subject will continue with the randomization number and study medication. The study staff will notify the Sponsor Contact as soon as the error is discovered without disclosing the study medication administered. Admission of subsequent eligible subjects will continue using the next unallocated number in the sequence.

The study will be conducted at investigative sites in multiple countries and will likely involve variable numbers of subjects at each site. Enrollment will be on a competitive basis but each site will be capped at 48 subjects per site. Activation of investigational sites in each country will be centrally controlled by a centrally managed Interactive Web Response system (IWRS).

Eligible subjects who complete the run-in period and meet all study inclusion/exclusion requirements will be randomized in a 2:1 ratio to receive investigational product. Subjects will be assigned to treatment arms in sequential order as they qualify for the study, using the IWRS. Randomization will be stratified according to baseline HbA_{1c} ($\leq 9.5\%$ or $> 9.5\%$ at screening visit), baseline eGFR (eGFR < 60 or ≥ 60 mL min⁻¹ per 1.73 m² at screening), BMI (< 25 kg m⁻² or ≥ 25 kg m⁻²) and history of heart failure (yes or no).

Among the 3 groups of subjects based on the baseline CV risks, a minimum of 352 subjects (21%) from each of the three groups will be recruited and ≤ 400 subjects who have a history of heart failure can be randomized in the study. If a subject has a history of class

II or III heart failure, the subject will be allocated to group 2, regardless of any history of atherosclerotic vascular disease or additional cardiovascular risk factors. If a subject does not have a heart failure history and has a history of atherosclerotic vascular disease, the subject will be allocated to group 1 regardless of other cardiovascular risks. Subject status with respect to group assignment criteria will be recorded on the CRF and group assignment will be stored in the IWRS. The final group assignment used in the summary or analysis will be primarily based on data captured in the IWRS. Subjects will be considered as CV risk group 2 if subject is assigned to group 2 on IWRS or satisfied group 2 criteria on CRF. Otherwise, CV risk group will be determined based on the assignment by IWRS.

3.8.2. Blinding

This is a double-blind placebo-controlled study. The sponsor, investigators, study coordinators, pharmacists, study subjects, and the CEC and DKA adjudication committee members will be blinded to the composition of the investigational product. Upon randomization, each subject will receive a subject randomization number and a drug kit assigned to the subject. To maintain blinding of the individual treatment assignments, central laboratory glucose urinalysis data will not be made available to any study personnel or subjects.

If knowledge of the investigational product ingredients is needed to manage the subject's condition, the investigator will contact the IWRS to obtain the treatment assignment. If unblinding occurs for any reason, the time and reason for breaking the blind will be recorded on the case report form (CRF) and the sponsor must be notified within 24 h.

A designated statistician who is not involved in the study operation will hold the treatment codes. The unblinded treatment information can be provided to the DSMB to facilitate the evaluation of any clinically important increase in the rate of a serious suspected adverse reaction or to the designated safety contact when the treatment information is required to determine if an expedited safety report must be submitted to regulatory agencies.

The treatment assignment will continue to be withheld from the cardiovascular endpoint committee (CEC) members until all investigational studies contributing to the MACE+ meta-analysis are completed and the meta-analysis has been conducted.

3.9. ADMINISTRATION OF STUDY MEDICATION

The following investigational products (IP) will be used for oral administration:

- Bexagliflozin tablets, 20 mg: tablets containing 20 mg of bexagliflozin
- Bexagliflozin tablets, placebo: tablets containing no bexagliflozin

Bexagliflozin tablets, 20 mg or placebo, should be taken in the morning prior to eating or drinking. The tablets should be taken with 250 mL of water.

Dosing with bexagliflozin tablets, 20 mg or placebo, will be based on randomized assignment. All study subjects will be instructed to self-administer tablets once daily in the morning prior to eating or drinking; the medication should be taken with water. There will be no change of dose during the treatment period.

On the day of each scheduled clinic visit, subjects must fast for a minimum of 10 hours prior to the collection of blood samples. During the fasting period, only water will be permitted. The investigational product should be administered at the clinic under supervision on the day of visit V2 when the run-in drug is dispensed and on the day of visit V3 when the double-blind study drug is dispensed. Only one tablet per day should be administered.

3.10. STUDY PROCEDURES AND FLOWCHART

The study activities at each clinic visit are presented in Table 2 and Table 3. The schedule of laboratory tests is presented in Table 4.

A visit window of ± 3 days is allowed for all visits except Visit 3. Visit 3 is the day of randomization and the basis for the visit window.

The study staff will contact each subject prior to a scheduled clinic visit to confirm the time of the visit and to remind the subject of proper fasting practice. A subject must be queried to assess compliance with a minimum 10 hours fast prior to blood draw to ensure the FPG and triglycerides values can be accurately determined. If a subject has not fasted for 10 hours, the subject must return as soon as can be arranged (within 1 week) to provide a specimen after proper fasting. Urine samples will be transported to the central lab for urinalysis.

Table 2 Schedule of Events from Screening to Week 48

Procedure	Screening	Run-in	Treatment Period							
	V1	V2	V3	V4	V5	V6	V7	V8	V9	V10
Visit number	V1	V2	V3	V4	V5	V6	V7	V8	V9	V10
Time to Randomization Visit (weeks) ¹	-2 to -5	-2	0	2	6	12	18	24	36	48
Type of visit ²	C	C	C	P	C	C	P	C	C	C
Informed Consent	X									
Screening for I/E criteria	X		X							
Demographics and medical history	X									
Diet & exercise counseling ³		X								
Physical exam ⁴	X		X			X		X	X	X
Weight and height ⁵	X	X	X		X	X		X	X	X
Diary & glucometer record review ⁶		X	X	X	X	X	X	X	X	X
Dispense Run-in Medication		X								
Randomization			X							
Vital signs	X		X		X	X		X	X	X
ECG	X		X					X		X
Dispense study medication ⁷			X			X		X	X	X
Blood draw for clinical lab test ⁸	X		X		X	X		X	X	X
Population PK sampling ⁹					X	X				
Urine collection ¹⁰	X		X		X	X		X	X	X
AE and potential DKA		X	X	X	X	X	X	X	X	X
Con Med		X	X	X	X	X	X	X	X	X

Table 3 Schedule of Events after Week 48 to End of Study

Procedure	Treatment Period			Follow Up
	Visit number	V 12, 14, 16, 18, etc.	EV	FU
Time to Randomization Visit (weeks) ¹	V 11, 13, 15, 17, etc. 60, 84, 108, 132, 156, etc.	V 12, 14, 16, 18, etc. 72, 96, 120, 144, 168, etc.	End of treatment visit	4 weeks after EV
Type of Visit ²	P	C	C	C
Informed Consent				
Screening for I/E criteria				
Demographics and medical history				
Diet & exercise counseling ³				
Physical exam ⁴		X	X	X
Weight and height ⁵		X	X	X
Diary & glucometer record review ⁶	X	X	X	X
Dispense Run-in Medication				
Randomization				
Vital signs		X	X	X
ECG		X	X	X
Dispense study medication ⁷		X		
Blood draw for clinical lab test ⁸		X	X	X
Population PK sampling ⁹				
Urine collection ¹⁰		X	X	X
AE and potential DKA	X	X	X	X
Con Med	X	X	X	X

Footnotes for the Schedules of Events:

- 1 Screening period may last up to 3 weeks (V1 to V2); run-in period is to be 2 weeks (V2); the efficacy assessment period (V3 to V8) will be 24 weeks; the total treatment period will be 104 to 156 weeks. A visit window of ± 3 days is allowed for all visits except visit V3. Visit V3 is to be scheduled between 13 and 15 days after visit V2 is complete. Visits V4 and V7 will be phone interviews.
- 2 Visits will be conducted as phone interviews (P) or clinic visits (C).
- 3 Diet and exercise counseling will be performed at V2.
- 4 A complete physical examination will be performed by the investigator at V3 prior to randomization and at the follow up visit (FU). Abbreviated physical examinations will be performed by the investigator at all other time points, unless clinically indicated. During the abbreviated physical examinations, general assessment of the skin, heart, lungs and abdomen will be performed.
- 5 Weight will be determined at all clinic visits and height will be determined at screening visit only (V1).
- 6 Glucometer will be dispensed to each enrolled subject at visit V2. Glycemic control diary will be dispensed at visit V3. Subjects will be trained on using glucometer and SMBG recording. SMBG record will be reviewed by the investigator at all subsequent visits including both phone interview and clinic visits.
- 7 One bottle of the investigational product will be dispensed between V3 and V8. Two bottles of the investigational product will be dispensed between V12 and end of treatment visit EV.
- 8 Blood sample collection and laboratory tests at designated visits are listed in Appendix 2 of the protocol. A minimum fasting time of 10 h must be confirmed prior to blood draw.
- 9 PK samples will be drawn in selected subjects in participating trial centers only. The samples will be drawn during the weeks 6, and 12.
- 10 Urine pregnancy test (UPT) is scheduled for all women at screening and just for WOCBP thereafter.

Table 4 Schedule of Laboratory Tests

Procedure	Screening	Treatment						Follow up
		V1	V3	V5	V6	V8, 9, 10	V 12, 14, 16, 18, etc.	
Time to Randomization Visit (weeks)		0	6	12	24, 36, 48	every 24 weeks	End of treatment	
Hematology ¹	X	X		X	X	X	X	X
Serum chemistry electrolytes ¹	X	X		X	X	X	X	X
Fasting Plasma Glucose ¹	X	X	X	X	X	X	X	X
HbA _{1c} ¹	X	X	X	X	X	X	X	X
Lipids ^{1, 2}	X	X		X	X	X	X	X
Urinalysis ³	X	X	X	X	X	X	X	X
UACR ⁴	X	X			X	X	X	
Infectious disease testing ⁵	X							
Urine pregnancy test (UPT) ⁶	X	X	X	X	X	X	X	X
PK sampling ⁷			X	X				
Biomarker sampling		X		X				
NT-proBNP sampling ⁸	X							

- 1 Blood for clinical chemistry and hematology will be drawn after 10 h of fasting prior to breakfast (i.e. only water is allowed).
- 2 LDL-C will be calculated by the Friedewald equation. At screening, the calculated LDL-C value is invalid by this equation and will be set as missing if triglycerides are > 400 mg dL⁻¹. Direct LDL-C will be determined in subjects whose baseline triglycerides are > 350 mg dL⁻¹. All subsequent LDL-C of these subjects will be determined by the same direct LDL-C measurements only.
- 3 Urine samples will be collected at all clinic visits. Glucose in the urinalysis results must be suppressed from the laboratory report so the dosing blind can be maintained. Testing strips with only the leucocytes and nitrate will be provided for immediate assessment at the sites.
- 4 UACR will be determined at screening V1, V3, and every 24 weeks until the end of treatment visit is conducted.
- 5 Infectious disease testing will be conducted at screening only. HIV testing will be conducted at screening in Canada.

- 6 UPT will be performed for WOCBP at all clinic visits. For surgically sterile or post- menopausal women, it will only be done at Visit V1.
- 7 Samples for the PK analysis will be drawn at weeks 6 and/or 12 from 240 subjects who consent to the PK study in participating trial centers.
- 8 Samples for NT-proBNP evaluation will be drawn within 1 h of the ECG measurement during the screening (V1) visit for Group 2 subjects with undocumented ejection fraction or documented left ventricular ejection fraction (LVEF) > 40%.

4. ENDPOINTS

4.1. PRIMARY EFFICACY ENDPOINT

- Change in HbA_{1c} from baseline to week 24, compared to placebo

4.2. SECONDARY EFFICACY ENDPOINTS

The key secondary efficacy endpoints include:

- Change in HbA_{1c} from baseline to week 24 in randomized subjects who have been prescribed insulin to control their diabetes
- Change in body weight from baseline to week 48 in subjects with a BMI $\geq 25 \text{ kg m}^{-2}$
- Change in SBP from baseline to week 24 in subjects with baseline systolic blood pressure $\geq 140 \text{ mm Hg}$

The exploratory secondary efficacy endpoints include:

- Change from baseline in HbA_{1c} over time
- Change from baseline in FPG over time
- Change from baseline in body weight over time
- Change from baseline in SBP over time
- Requirement of additional anti-diabetic medications, including insulin; and time to first use of additional anti-diabetic medication
- Requirement of reduced anti-diabetic medications, including insulin dose over time; and time to first reduced anti-diabetic medications
- Hospitalization for heart failure in all subjects and in subjects with a history of heart failure
- Time to hospitalization for heart failure in subjects in all subjects and in subjects with a history of heart failure
- Time to hospitalization for heart failure or cardiovascular death in all subjects and in subjects with a history of heart failure
- Change in HbA_{1c} from baseline to week 24 in randomized subjects who have been prescribed sulfonylurea without insulin to control their diabetes

4.3. SAFETY ENDPOINTS

The key safety endpoints include:

- A 5-point composite endpoint of CV death, non-fatal myocardial infarction, non-fatal stroke, hospitalization for unstable angina, or coronary revascularization
- A 6-point composite endpoint of CV death, non-fatal myocardial infarction, non-fatal stroke, hospitalization for unstable angina, coronary revascularization or hospitalization for heart failure
- Individual events including all-cause mortality, CV death, fatal and non-fatal myocardial infarction, fatal and non-fatal stroke, hospitalization for unstable angina, hospitalization for CHF, or coronary revascularization. Both first events and total events, taking account of repeat events will be examined
- Change in eGFR from baseline
- Change in UACR from baseline
- Incidence of adverse events of interest. Adverse events of interest including urinary tract infections (UTI), pyelonephritis urosepsis, genital mycotic infections (GMI), diuretic effects including hypovolemia, hypotension episodes, hypoglycemia, hepatotoxicity, fractures, malignancies, hypersensitivity reactions, acid-base disorders including diabetic ketoacidosis, rash, renal failure events, and amputations

Other safety endpoints include:

- Adverse events
- Clinical laboratory events
- Physical examinations
- Vital signs including orthostatic blood pressure
- Use of concomitant medications

4.4. OTHER ENDPOINTS

Samples for population PK analysis will be collected and the plasma concentration of bexagliflozin determined. The PK parameters will be assessed separately as part of the population PK analysis. Biomarker samples will be collected. The biomarker analysis will be performed separately. These analyses will not be discussed in this SAP.

5. ANALYSIS SETS

5.1. SCREENED ANALYSIS SET

The screened analysis set will include all subjects who have signed the informed consent forms and completed the eligibility screening prior to randomization. The screened population will consist of both enrolled subjects and subjects who do not meet the eligibility criteria. Unless specified otherwise, this population will be used for summaries of subject disposition.

5.2. SAFETY ANALYSIS SET

All subjects who are randomized and take at least one dose of the double-blind IPs will be included in the Safety Analysis Set. Safety analyses will be based on the medication that was actually dispensed to each subject. This is the primary analysis set for safety. If a randomization error causes a subject in the placebo arm to receive active drug inadvertently, the subject will be considered exposed to active drug and will be analyzed accordingly in the Safety Analysis Set. If a subject in the active arm receives placebo inadvertently but receives active drug subsequently, the subject will be considered exposed to active drug and will be analyzed accordingly.

5.3. INTENTION-TO-TREAT ANALYSIS SET

All subjects who are randomized regardless of treatment adherence or availability of follow up data will be included in the intention-to-treat analysis set (ITT). All analyses of the ITT will be based on each subject's randomized assigned treatment by the IWRS.

5.4. PER PROTOCOL ANALYSIS SET

The Per Protocol (PP) Analysis Set will include all subjects in the ITT who meet the study eligibility requirements and have no major protocol deviations that will affect the validity of the efficacy measurements. Detailed protocol deviations that may result in subject or visit exclusion from the PP Analysis Set are described in Section 5.5. The subject assignment to the PP analysis set will be determined prior to database lock. The PP Analysis Set will serve as the secondary set for efficacy assessment.

5.5. PROTOCOL DEVIATIONS

Protocol deviations will be captured during monitoring visits. Major protocol deviations that could affect the primary and secondary variables, in the opinion of the medical monitor, will be considered when determining a subject's eligibility for the PP population. Table 5 describes some possible types of major protocol deviations. All protocol deviations will be reviewed and determined as major or minor before database lock.

Table 5 Some Possible Types of Major Protocol Deviations

Category	Criteria	Exclusion
Inclusion/Exclusion Criteria		
Ineligible subject is enrolled	- Subjects not satisfying HbA _{1c} inclusion criteria - Treated with SGLT2 within 3 months of screening	Subject exclusion
Prior or Concomitant Medication Restrictions		
Use of another SGLT2 inhibitor	Use of an SGLT2 inhibitor as the rescue medication for hyperglycemia	Visit exclusion [exclude data post SGLT2 starts]
Dosing Non-Compliance		
Dosing Non-Compliance	-Subject missed more than 50% of the investigational product doses between week 12 and week 24	Subject exclusion

5.6. SUBSETS

Subsets below will be repeated for selected analyses:

- Subjects who have been prescribed insulin: This subset includes all subjects who are taking insulin (ATC class 3 is A10A - INSULINS AND ANALOGUES FOR INJECTION, LONG-ACTING) on the day that the subject took the first dose of the study medication. This subset will be used in the baseline demographics, analyses of primary and key secondary efficacy endpoints, adverse event, clinical lab, and vital signs in addition to all subjects.
- Subjects who have been prescribed sulfonylurea: This subset includes all subjects who are taking sulfonylurea (ATC class 4 is A10BB - SULFONYLUREAS) and not taking insulin on the day that the subject took the first dose of the study medication. This subset will be used in the analysis for primary and key secondary efficacy endpoints, adverse event, clinical lab, and vital signs in addition to all subjects.
- Subjects with a history of heart failure: This subset includes all subjects who indicate they had a history of congestive heart failure at screening on CRF cardiovascular disease history page. This subset is primarily used in the analyses on heart failure related exploratory endpoints.

6. GENERAL ASPECTS FOR STATISTICAL ANALYSIS

6.1. GENERAL METHODS

The proposed statistical methodology and analyses are in accordance with the principles outlined by the ICH E9 guidelines. All statistical analyses will be conducted using SAS statistical software version 9.3 or higher.

Tables, listings and figures (TLFs) will be produced in accordance with the principles outlined by the ICH E3 guidelines. For most summary statistics, data will be analyzed by the following treatment arms: Bexagliflozin 20 mg and Placebo. All available data from subjects who signed an informed consent will be presented in the subject listings.

Data summaries will use descriptive statistics (number of subjects [n], mean, standard deviation [SD], Q1, median, Q3, minimum and maximum) for continuous variables, and frequency and percentage of subjects for categorical and ordinal variables, unless otherwise specified.

Unless otherwise specified, all statistical tests will be one-tailed using a 0.025 level of significance. All confidence intervals (CIs) will be two-sided 95% CIs.

The analysis visit window will be assigned to data collection. One selected data point per visit will appear in summary tables and figures. Refer to section 6.4 for details. All visit assessment data will be included in shift tables and will appear in the subject listings.

No data imputation will be applied for missing values, unless otherwise specified.

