- A 6-point composite endpoint of CV death, non-fatal MI, non-fatal stroke, hospitalization for unstable angina, coronary revascularization or hospitalization for heart failure
- Individual events including all-cause mortality, CV death, fatal and non-fatal MI, fatal and non-fatal stroke, hospitalization for unstable angina, hospitalization for CHF, or coronary revascularization. Both first events and total events, taking account of repeat events will be examined
- Change in eGFR from baseline
- Change in UACR from baseline
- Incidence of adverse events of interest. Adverse events of interest including urinary tract infections including urosepsis and pyelonephritis, genital mycotic infections, diuretic effects including hypovolemia, hypotension episodes, hypoglycemia, hepatotoxicity, falls and fractures, malignancies, hypersensitivity reactions, acid-base disorders, renal failure events, and amputations

Other safety assessments:

- Adverse events
- Clinical laboratory events
- Physical examinations
- Vital signs including orthostatic blood pressure
- Use of concomitant medications

Statistical Methods:

The primary endpoint is the difference in the change in HbA1c from week 0 (randomization visit) to week 24 among subjects exposed to bexagliflozin, 20 mg, compared to subjects exposed to placebo. Statistical significance will be declared at a two-sided 0.05 level of significance. The intention-to-treat population that includes all randomized subjects regardless of treatment adherence or availability of follow-up data will be analyzed. A mixed model repeated measures (MMRM) analysis of covariance model (ANCOVA) with baseline HbA1c as a covariate will be performed on the available data, incorporating all visits from

each patient at which HbA1c was measured.

Three key secondary endpoints are:

1. Change in HbA1c from baseline to week 24 in randomized subjects who have been prescribed insulin to control their diabetes
2. Change in body weight from baseline to week 48 in subjects with a BMI ≥ 25 kg/m²
3. Change in SBP from baseline to week 24 in subjects with baseline systolic blood pressure ≥ 140 mmHg

A hierarchical testing strategy in the following order will be undertaken, if the null hypothesis is excluded for the primary efficacy endpoint:

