9 PLANNED STATISTICAL METHODS

9.1 General Considerations

The following sections provide a summary of the planned analysis of the trial but a full analysis plan will be developed as a separate document and will become the final plan. All statistical analyses will be performed using SAS Version 9.4 or higher.

Data summaries will use descriptive statistics (number of subjects [N], mean, standard deviation [SD], Q1, median, Q3, minimum, and maximum) for continuous variables, and frequency and percentage of subjects for categorical and ordinal variables. If there are missing values, the number missing will be presented, but without a percentage.

Unless otherwise specified, all tests will be two-tailed using a 0.05 level of significance. All confidence intervals (CIs) will be two-sided 95% confidence intervals.

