9.5.3 Multiple Comparisons / Multiplicity

A sequential testing procedure will be applied to the testing of the treatment differences of the primary and key secondary efficacy endpoints, to control the familywise error rate at a two-sided 5% level. Each comparison will be done based on the pre-specified testing hierarchy, so multiplicity adjustment will not be performed.

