8.1. PRIMARY EFFICACY ENDPOINT AND ANALYSIS

The primary efficacy hypothesis is that bexagliflozin reduces HbA_{1c} after 24 weeks of treatment when compared to placebo.

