8.2.2. Exploratory secondary efficacy endpoints and analyses

All endpoints in this section are exploratory. No sensitivity analyses and adjustment for multiple comparisons will be conducted. Nominal p-values will be used to examine any trends in these endpoints.

8.2.2.1. Change in HbA_{1c} from baseline to week 24 in randomized subjects who have been prescribed sulfonylurea to control their diabetes

Same MMRM ANCOVA model as in section 8.1.1 will be used for this analysis. Analysis will be conducted based on ITT and PP analysis set. Same sensitivity analysis as in section 8.1.2 will be repeated. Subgroup analysis will be conducted by baseline HbA_{1c} category and baseline eGFR categories.

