8.2.2.6. Time to first use of intensification or relaxation of hypoglycemic agent

Kaplan-Meier plots will be prepared for these endpoints by treatment. These endpoints will be analyzed using Cox proportional hazards models with treatment, region, baseline eGFR categories (<60 or ≥60 mL min⁻¹ per 1.73 m²), baseline BMI (< or ≥25 kg m⁻²), history of heart failure (yes or no), insulin use or not, and baseline HbA_{1c} as the covariates. Maximum likelihood with ties method of Breslow will be used. The hazard ratio of the endpoint, p-value with its two-sided 95% CIs presented. Subjects who withdraw from the trial and have post-baseline assessments will be censored at the last contact date. Subjects who have no follow-up event data will be censored at the date of randomization + 1 day. Analysis will also be conducted for subjects who have been prescribed insulin or sulfonylurea to control their diabetes. Time to first intensification of hypoglycemic agent will also be conducted for subjects who have been prescribed insulin or sulfonylurea to control their diabetes.

8.2.2.7. Time to hospitalization for heart failure and time to cardiovascular death or hospitalization for a heart failure event in all subjects and in subjects with a history of heart failure

Same analyses in Section 8.2.2.6 will be conducted. History of heart failure will not be used in the analysis model in subjects with a history of heart failure.

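### SAP 6.1 replaces the protocol's two-tailed 0.05 default with one-tailed 0.025 and does not declare it, so the exploratory p-values have no stated tail and are halved when favourable

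*Combined protocol and SAP*

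**What the plan says.** The protocol is two-sided for efficacy testing. Section 9.1 sets the default: "Unless otherwise specified, all tests will be two-tailed using a 0.05 level of significance". For the primary endpoint the synopsis states "Statistical significance will be declared at a two-sided 0.05 level of significance", and it repeats that level for each key secondary test. Section 9.5.3 describes the hierarchy as designed "to control the familywise error rate at a two-sided 5% level". Section 9.6.1 describes the insulin-subset power as two-sided.

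SAP 6.1 sets a different default, "Unless otherwise specified, all statistical tests will be one-tailed using a 0.025 level of significance", and follows it with "All confidence intervals (CIs) will be two-sided 95% CIs". SAP 3.7 recasts the insulin-subset power calculation at a one-sided 0.025 level. SAP 8.1 gives a direction for the primary endpoint, "The primary efficacy hypothesis is that bexagliflozin reduces HbA_{1c} after 24 weeks of treatment when compared to placebo", and 8.1.1 writes the matching one-sided null and alternative.

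For the exploratory endpoints, SAP 8.2.2 says "Nominal p-values will be used to examine any trends in these endpoints". It gives neither a threshold nor a direction. Section 8.2.2.6 covers time to intensification and time to relaxation and specifies "The hazard ratio of the endpoint, p-value with its two-sided 95% CIs presented". Section 8.2.2.7 applies the same analysis to heart-failure hospitalization and to heart-failure hospitalization or CV death.

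SAP Section 12 records the move from FAS to ITT, the covariate changes, the new imputation for the primary analysis and the added exploratory items. It does not record a change of sidedness.

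**The concern.** Protocol 9.1 makes the SAP the final analysis plan, so the SAP default governs what is reported. Nothing in 8.2.2 overrides it for the exploratory tests.

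Three things follow. First, a one-tailed p-value needs a chosen tail, and none is given for these endpoints. Intensification and relaxation share one rule, yet benefit would presumably mean fewer of the first and more of the second. Second, a reader who knows the protocol expects two-sided p-values. Nothing in the SAP's p-value formatting rules (Section 14) labels the sidedness, so a halved value can be mistaken for a two-sided one. Third, if the tail is taken to favour the drug, an excess of heart-failure events yields a large p-value. Heart-failure hospitalization and CV death are classed here as exploratory efficacy, but a reader will look at them for harm as well.

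**Working it through.** **1. Does the switch change any formal decision?**

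The two-sided 0.05 critical value is 1.95996 and the one-sided 0.025 value is 1.95996. They are identical.

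The plan's own figure for the insulin subset (SAP 3.7, protocol 9.6.1) is N = 800, effect 0.3%, SD 1.1%, more than 90% power. Assuming the 2:1 allocation carries over to the subset (about 533 and 267):

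- SE = 1.1 × sqrt(1/533.3 + 1/266.7) = 0.0825
- power = Φ(0.3/0.0825 − 1.96) = Φ(1.676) = 95.3%

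The stated figure is reproduced, with the same result under either rule. For the primary endpoint (1100 against 550, effect 0.22%, SD 1.1%), SE = 0.0574 and power = Φ(3.830 − 1.96) = 96.9%, again under either rule. The plan states 90%; sidedness does not explain that difference.

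**2. Do the one-tailed p-value and the two-sided CI agree?**

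In standard-error units, with negative values favouring the drug:

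| z | one-tailed p | two-tailed p | 95% CI |
|---|---|---|---|
| −2.0 | 0.023 | 0.046 | −3.96 to −0.04 |
| −1.8 | 0.036 | 0.072 | −3.76 to 0.16 |
| +2.5 | 0.994 | 0.012 | 0.54 to 4.46 |

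In the favourable direction, p < 0.025 holds exactly when the CI excludes zero. The two appear to conflict only when a one-tailed p-value is read against 0.05 (z between −1.96 and −1.645). In the harmful direction the p-value is near 1 while the CI excludes zero.

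**3. What this means for the heart-failure endpoints**

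Inputs: the two-year event table (SAP Table 1, protocol Table 2) projects 62 heart-failure hospitalizations and 58 CV deaths. The composite therefore has between 62 events (complete overlap) and 62 + 58 = 120 (no overlap). For D events split 2:1, SE(log HR) = 1/sqrt(D × 2/9).

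*D = 120:* SE = 0.194. For HR 0.72, z = ln(0.72)/0.194 = −1.70.

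- one-tailed p = 0.045; two-tailed p = 0.090
- 95% CI = exp(−0.329 ± 1.96 × 0.194) = 0.49 to 1.05

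*D = 62:* SE = 0.269. One-tailed p falls below 0.05 at HR = exp(−1.645 × 0.269) = 0.64. The CI excludes 1 only below exp(−1.96 × 0.269) = 0.59. Any hazard ratio between 0.59 and 0.64 prints p < 0.05 beside a CI that includes 1.

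*D = 62, harmful direction:* for HR 1.75, z = 0.560/0.269 = 2.08.

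- two-tailed p = 0.038; one-tailed p, tail favouring the drug = 0.981
- 95% CI = exp(0.560 ± 0.528) = 1.03 to 2.97

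**4. Can the default be applied everywhere?**

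No. SAP 8.1.1 reports p-values for model effects, and the model contains treatment-by-visit and a three-level region term. Tests of several degrees of freedom have no one-tailed form.

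**The case against.** The strongest reply is that the SAP is coherent at its own level. One-tailed 0.025 and a two-sided 95% CI are the same rule in the favourable direction, the default sentence carries the 0.025 as well as the tail, and a printed 0.045 is then not significant. The exploratory p-values are declared nominal and unadjusted, and no claim rests on them. Reading them against 0.05 is something a reader might do; the SAP does not invite it.

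Most of that stands, and it rules out several stronger readings.

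- A reader might infer that safety p-values are halved. SAP Section 9 names none. Adverse events of special interest get counts, percentages and rates; UACR gets LS means and CIs by arm; MACE+ and the CV time-to-event safety analyses are deferred to a meta-analysis plan.
- A reader might infer that the p-values contradict their own CIs. They do not at 0.025 in the favourable direction.
- A reader might infer that harm would be hidden. Only the p-value misses it: the CI of 1.03 to 2.97 for HR 1.75 appears in the same output.
- A reader might infer that every test is one-tailed. The sentence sets a default and allows exceptions.

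It is also fair to say that the display rules do not state which p-value will be printed, so the halving follows from applying 6.1 literally.

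What the reply does not answer is that the protocol says otherwise, that Section 12 is silent, and that no tail is stated for any exploratory endpoint.

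**Conclusion.** The contradiction is real and undeclared, and the SAP should be corrected. It is a consistency and reporting defect confined to the exploratory p-values. It does not threaten the primary or key secondary conclusions, and it does not inflate their error rate in the favourable direction.

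If SAP 6.1 is followed as written, favourable exploratory p-values are half the two-sided value that the protocol's default specifies. Harmful ones approach 1 if the tail favours the drug. For intensification and relaxation the tested direction is undefined.

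The heart-failure figures are illustrations with hazard ratios chosen to show the effect. They assume the two-year event projections, which apply a cited trial's placebo rates to both arms, a 2:1 split of events, and the usual approximation to the standard error of the log hazard ratio. The 120-event case ignores overlap between heart-failure hospitalization and CV death. That composite was added by the SAP, so the protocol reaches it only through its general two-tailed default.

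**What to change.** In SAP 6.1, restore two-tailed tests at 0.05, keep the two-sided 95% CIs, and state that all reported p-values are two-sided.

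That sentence alone is not enough. The one-sided 0.025 wording for the insulin endpoint in SAP 3.7 must be reconciled with the two-sided wording in protocol 9.6.1. If the one-sided hypothesis in SAP 8.1.1 stays, add that one-sided 0.025 is equivalent to two-sided 0.05 in the direction favouring bexagliflozin. List any one-sided testing that is retained in Section 12.

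The cost is a few sentences. Sample size, power, the testing hierarchy and the CIs are unchanged. The downside is that some nominal exploratory p-values become less favourable.
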